### **Research questions for Part B – ‘Perception of imposed performance variations’**

- Do PwMS with and without reported fatigue, and HC differ in their perceptive accuracy for imposed walking speed variations during treadmill-based experimental protocols? Are these difference modulated by the accumulation of fatigue during the course of the protocol?
- Do PwMS with and without reported fatigue, and HC differ in their perceptive accuracy for imposed STS vertical excursion variations during self-paced experimental protocols? Are these difference modulated by the accumulation of fatigue during the course of the protocol?
- Are these difference modulated by time (different subphases) within the course of the protocol?
- Do PwMS and HC differ in the correspondence between measured and subjective (i.e. confidence rating) dimensions of perceptive accuracy?

### **Hypothesis**

- PwMS and HC will differ in the measured outcomes of perceptive accuracy for imposed walking speed variations during treadmill-based experimental protocols, lower accuracy is expected in PwMS with higher reported fatigue
- PwMS and HC will differ in the measured outcomes of perceptive accuracy for imposed STS vertical excursion variations during self-paced experimental protocols, lower accuracy is expected in PwMS with higher reported fatigue
- PwMS will be less accurate than controls to a larger extend in the last subphase of the protocol (i.e. returning to comfortable speed or seat height levels from the most difficult performance level)
- Lower correspondence between measured and subjective (i.e. confidence rating) dimensions of perceptive accuracy is expected in PwMS

## Data and statistical analysis

Motor performance data (gait and STS kinematic, kinetics and spatial-temporal parameters) will be acquired by wearable sensors and extracted from Moveo software (APDM) as .csv file or raw data, and Matlab scripts will be used in case of parameters requiring specific calculation. Data acquired from the participants reports on their perception, during the experimental tasks in Part A and Part B, will be extracted with dedicated Matlab scripts. Statistical analysis will be performed using SPSS (V. 28.01). Tests of normality (Shapiro-Wilk test) will be used to determine if parametric or non-parametric statistical tests have to be used for the comparisons and correlations. The  $\alpha$  for all analyses will be set at 0,05.

**Clinical assessment** outcomes, with a particular focus on the MAIA-2, ISAQ and PAS scores and subscores, will be compared between groups with an independent T test (or with its non-parametric equivalent Mann-Whitney U-Test), to detect significant differences in the subjective beliefs about perceptive abilities.

In the **experimental Part A** we will obtain the participants' minimal perceptive threshold for self-paced performance variations which will be compared between groups with an independent T test (or with its non-parametric equivalent). We will also relate the frequency of the reports with the measured performance variability (coefficient of variation of the selected motor performance parameter: gait speed or STS duration) to obtain a novel outcome measure reflecting perceptive accuracy. We will study it between and within groups using a mixed model ANOVA with time and group as factors to detect significant differences between PwMS and controls and its variations relative to the accumulation of fatigue during the prolonged motor tasks. To investigate its interference with perceptive accuracy the difference between the subjective rate of fatigue (VAS-F) pre-post task protocols will be included in the analysis as covariate.

In the **experimental Part B** within-subject correlations will be calculated between the imposed performance in motor tasks and the perception of its variations. These correlations will be examined separately for different phases of each trial to index perceptive accuracy. Fisher Z transformations (or other types of transformations eg. log transformation) will be applied to these correlations before further analysis, with results back-transformed for reporting. We will study it between and within groups using a mixed model ANOVA with time (protocol subphase) and group as factors to detect significant differences between PwMS and controls and its variations relative to the different subphases of the protocol. To investigate its interference with perceptive accuracy the difference between the subjective rate of fatigue (VAS-F) pre-post protocols will be included in the analysis as covariate. The correspondence between measured and reported dimensions of perceptive accuracy will be calculated as their absolute difference and compared between groups using an independent T test (or with its non-parametric equivalent).

Finally, for the accuracy outcomes derived from both experimental parts we will explore correlations, separated per group, to investigate the relationship between objectively measured perceptive accuracy and factors that potentially interfere with it (demographics, questionnaires and clinical assessments). Then, a regression analysis will be performed to assess the strength of these relationships and identify the most important explanatory factors or predictors.

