## Methodology

### Participants

44 PwMS and 44 healthy controls (40, +10% to cover possible dropouts and missing data) will be recruited from the Flemish MS rehabilitation centers in Melsbroek (NMSC) and Pelt (Noorderhart RMSC), and as well from the REVAL research center in UHasselt and its established network (eg. UMSC Patient Platform). Information flyers will be distributed in the centers and online content via the website and social media of REVAL and the Flemish MS society; no economical compensation will be provided by the research organization to the participants of this study. We will search age and sex-matching subjects for the healthy controls, considering a 5-year range per subject. After giving informed consent, demographics of age and gender, height and weight, years of education, as well as MS-related information such as EDSS, type of MS, use of assistive device for walking in daily life, and years since diagnosis, will be collected and provided by the centers or via self-report. The participants will be instructed to keep their normal routine but to avoid extraneous physical activity at least 24 hours before the data collection session.

- Inclusion criteria for PwMS: age between 18 and 65 years old; a diagnosis of MS (2017 revisions of the McDonalds criteria); ability to walk for 6 minutes without rest and without the need of a walking aid; ability to repeatedly perform the sit to stand transitions on a standard chair (43cm seat height) without hand support. Additionally, no relapses >1 month preceding the start of the study.
- Inclusion criteria for healthy controls: age between 18 and 70 years old, sex- and age-matched on a group level.
- Exclusion criteria: cognitive impairment hindering understanding of study instructions, pregnancy, and musculoskeletal disorders in the lower limbs (not related to MS), cardiovascular red flags for exercise (screened with Physical Activity Readiness Questionnaire), other diagnosis for neurological or metabolic disease limiting the full execution of the tests (eg. peripheral neuropathy altering the foot plantar sensibility).

Inclusion/exclusion criteria will be controlled at the beginning of the first session: the participant will read the criteria presented in the informed consent and will be asked to confirm that he/she can enroll in the study.

[figure not shown]

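### The planned comparisons of people with MS and healthy controls leave out age and sex, the matching variables, and in Part A the counterbalanced instruction order; adding them is a cheap, modest improvement

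*Combined protocol and SAP*

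**What the plan says.** Under Participants the protocol describes matching in two ways. One sentence reads "We will search age and sex-matching subjects for the healthy controls, considering a 5-year range per subject". The inclusion criteria for controls then ask for matching on sex and age at group level, with no tolerance. The age limits differ: "Inclusion criteria for PwMS: age between 18 and 65 years old", against an upper limit of 70 for controls.

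The introduction to Part A says that the two instruction sets (attend to quantity or to quality of performance) are given in counterbalanced order at group level. It does not say whether this is done within PwMS and HC separately.

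Data and statistical analysis specifies these group comparisons:

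- Questionnaires: the clinical measures, "with a particular focus on the MAIA-2, ISAQ and PAS scores and subscores, will be compared between groups with an independent T test", with Mann-Whitney as the alternative.
- Part A threshold: the "minimal perceptive threshold for self-paced performance variations which will be compared between groups with an independent T test", or its non-parametric equivalent.
- Part A accuracy: studied "using a mixed model ANOVA with time and group as factors to detect significant differences between PwMS and controls", with pre-post change in VAS-F as covariate.
- Part B accuracy: a "mixed model ANOVA with time (protocol subphase) and group as factors", with the same VAS-F covariate.
- Correspondence between measured and reported accuracy: an absolute difference, "compared between groups using an independent T test", or its non-parametric equivalent.

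Age, sex and instruction order appear in none of these. Demographics enter only afterwards, in exploratory correlations run separately in each group and a follow-on regression to identify explanatory factors.

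**The concern.** Groups made similar on age and sex by design have a difference in means that varies less than an independent t test assumes. The test still charges age and sex variation to error, so it is conservative and loses power. The same holds for a balanced instruction order in Part A.

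Balance is also not assured. The groups are not randomised, the two matching statements are not reconciled, and the group-level one has no tolerance. If controls end up older or younger on average and age predicts the outcome, an unadjusted comparison attributes part of the age effect to MS. The plan itself lists demographics among the factors that may interfere with perceptive accuracy, so an age or sex effect is plausible on its own terms. The per-group correlations and the regression are not described as adjusting the group contrast, so they do not close the gap.

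**Working it through.** **Inputs from the documents.** 40 evaluable per group, recruited as 44, and alpha 0.05. The plan's figure reproduces: 40 × 1.10 = 44. No effect size, SD or power is given for the 40.

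**Assumptions.** Two-sided testing; 40 v 40; R² for age, sex and order of 0 to 0.20; age SD of 10 or 13 years. The documents give none of these except the 40.

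**1. Precision if balance is exact.** Power comes from the noncentral t with noncentrality d / √[(1 − R²) × 2/40]. Degrees of freedom are 78 unadjusted and 78 − 3 = 75 with age, sex and order.

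| Analysis | Detectable d (80% power) | Power at 0.5 SD |
|---|---|---|
| Unadjusted | 0.634 | 0.598 |
| Adjusted, R² 0 | 0.635 | 0.598 |
| Adjusted, R² 0.05 | 0.635 × √0.95 = 0.619 | 0.620 |
| Adjusted, R² 0.20 | 0.635 × √0.80 = 0.568 | 0.694 |

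Under exact balance the true type I error of the unadjusted t test is 2 × [1 − T78(1.991/√(1 − R²))]. This is about 0.045 at R² 0.05 and 0.029 at R² 0.20, which is the conservatism described above.

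**2. Bias if an age gap remains.** Spurious group shift in SD units = √R² × gap / age SD. For R² 0.10 to 0.20:

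- 2.5-year gap: from 0.316 × 2.5/13 = 0.061 to 0.447 × 2.5/10 = 0.112 SD.
- 5-year gap: from 0.316 × 5/13 = 0.122 to 0.447 × 5/10 = 0.224 SD.

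Simulated type I error with no true difference, t test against a linear model with group, age and sex:

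| Mean age gap | Group-level matching, unadjusted | Per-subject matching, unadjusted | Adjusted |
|---|---|---|---|
| 2.5 years | 0.060–0.081 | about 0.05 or slightly below | near 0.05 |
| 5 years | 0.085–0.168 | 0.072–0.138 | near 0.05 |

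Per-subject matching gives lower figures because pairing makes the test conservative, which offsets part of the bias.

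**3. Instruction order (Part A).** An order effect of δ SD, balanced within groups, adds δ²/4 to the error variance: 1% for δ = 0.2 and 4% for δ = 0.4. If the orders split 24/16 in one group and 16/24 in the other, the bias is δ × (24 − 16)/40, or 0.06–0.10 SD for δ = 0.3–0.5. The δ values and the split are assumptions.

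**4. Cost if the covariates explain nothing.**

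- Average chance imbalance on three covariates multiplies the variance of the group difference by 1 + 3/74 = 1.041. Power at 0.5 SD falls from 0.598 to 0.581.
- Under that imbalance the covariates must explain 1 − 1/1.041, about 4% of variance, before adjusting gains anything. The detectable difference is then 0.631 at R² 0.05 and 0.579 at R² 0.20.
- A 5-year age gap multiplies the standard error by √[1 + (5/SD)²/4], which is 1.018 at SD 13 and 1.031 at SD 10. Power at 0.5 SD is then 0.572–0.583 at R² 0.

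**The case against.** The strongest reply is that the design already deals with these variables. Age and sex are matched, order is counterbalanced to limit order effects, and the study calls itself exploratory. Omitting covariates is then a matter of efficiency. With balance, the planned tests are indeed valid. But matching that the analysis ignores makes those tests conservative, and nothing in the analysis protects against whatever imbalance remains.

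Other parts of the reply stand:

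- The R² is unknown. Several outcomes are scaled to the person: the speed and seat-height ranges are personalised, Part A accuracy relates report frequency to the participant's own variability, and Part B uses within-subject correlations. Such scaling may remove some of the age or sex effect, so R² 0.20 could be optimistic.
- Adjustment is not free, as step 4 of the working shows.
- A reader might infer from the limits of 65 and 70 and the per-subject rule that controls may well average 5 years older. That needs a plus-or-minus-5 reading with every control at the same edge of the tolerance, and it would conflict with the group-level statement. The rule can also be read as a total width of 5 years, so at most 2.5 either side. The 5-year rows show an extreme, not an expectation.
- The calculations cover between-group contrasts. The hypothesis that PwMS lose more accuracy in the last Part B subphase is a group-by-subphase effect. It is tested against within-subject error, which age and sex main effects do not reduce, so no gain is shown there.

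**Conclusion.** The omission is plain in the text and applies to every specified PwMS v HC comparison, though the mixed ANOVAs do carry VAS-F change. Adjusting is the better choice, but the point is minor. For assumed R² of 0.05 to 0.20 the gain is small to moderate, and at R² 0 there is a small loss. The protection against bias matters mainly if matching is run only at group level and leaves a gap of a few years. It covers measured age and sex only, not other differences between PwMS and HC.

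Three stronger readings are not supported:

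- The planned tests are not invalid as they stand; that depends on the balance achieved.
- Because the clinical session and Part A may share a day, a reader might infer that session format is a further confounder. The documents show neither unequal uptake between groups nor an effect of the shared day.
- Because the research questions name PwMS with and without fatigue, a reader might infer a biased subgroup test. The analysis section specifies no such contrast, so there is no planned test to size.

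**What to change.** 1. For the MAIA-2, ISAQ and PAS scores and subscores, the Part A threshold and correspondence, replace the independent t test by a linear model with group, age (continuous, centred) and sex.
2. Keep the mixed ANOVAs for Part A and Part B accuracy, with VAS-F change as planned, and add centred age and sex.
3. Add instruction order (quantity first or quality first) to all Part A models, including correspondence computed from Part A data. State that order is counterbalanced within PwMS and HC separately.
4. If residuals are not normal, fit the same model to rank-transformed outcomes in place of Mann-Whitney, which cannot take covariates. For Part B the plan says "Fisher Z transformations (or other types of transformations eg. log transformation) will be applied to these correlations before further analysis"; name Fisher Z alone, because a log cannot be taken of a zero or negative correlation.
5. Reconcile the per-subject and group-level matching statements into one rule with its tolerance in years, and report the age and sex balance achieved.
6. If fatigue subgroups are compared, use the same covariates.

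The cost is a change of SAP wording, plus a sentence in the protocol on matching and one on counterbalancing. Age and sex are already collected, and order has to be assigned to be counterbalanced, so no new measurement is needed. The models spend 3 degrees of freedom in Part A and 2 elsewhere. The power cost is that in step 4 of the working, and close matching should keep it below the chance-imbalance figure.

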#### **Task 1: Perceptive accuracy for walking speed variations during overground 6MWT**

The participants will be tested overground, during a 6MWT, for their ability of accurately perceive changes in their self-paced gait speed: they will be instructed to walk for 6 minutes at the maximal speed that they can maintain safely and reporting any perceived oscillation in their own speed by squeezing the handheld sensor. The reason for the selected modality to acquire patient reports is that holding the sensor in the hand can serve as a reminder for the ongoing perceptive task, ensuring a continuous attention toward their speed and acquisition of reports (the action of holding the sensor, without squeezing it, confirms that the participant is not perceiving any change in speed, accordingly to the received standardized instructions).

Neutral instructions will be provided to the subject before starting the 6MWT by reading the following script: "When you will hear the beep tone, squeeze the sensor and start walking at the maximal speed that you can maintain safely for the 6 minutes-length of the experiment. During this period, but only for the straight parts of the walking track, please pay attention to your walking speed. Natural variations in your walking speed may occur during the test. We want you to notice, and report them using the handheld sensor being them accelerations or decelerations, this information does not matter for our test and therefore you will not have to indicate it: as soon as you perceive a change in your walking speed, squeeze the sensor in your hand to save your report. Report only changes in speed that you perceived during the straight parts of the walking tract: all the

variations that are due to the turning will be cut out from the analysis. If you will squeeze during a turn, that report will be saved as if it was given three steps before the turn.

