Participants will be also equipped with noise-cancelling headphones to avoid auditory perception of steps rhythm and influence of possible environmental distractions. Using wearable sensors to detect motor performance (spatiotemporal and kinematic parameter detected with a configuration of 6 OPALS – technology© IMU sensors: 2 over the dorsal part of the feet, 2 on the lower legs, 1 anterior to the sternum and 1 posterior to the third/fourth lumbar vertebra, see figure 4) will allow us to then compare the time and frequency of the reports with the actual speed variations, cutting out the steps executed while turning, and propose novel outcome measures: the change in speed at the first report as a perceptive threshold for overground walking speed changes, informing on the minimal clinically important change, and the ratio between reporting frequency and actual speed variability, reflecting perceptive accuracy (see example plot in Figure 6).

[figure not shown]

Figure 6 Perceptive accuracy for walking speed variations during overground 6MWT: Task 1 illustration, wearables placement and Perception vs Performance plot graphic illustration

The intensity of perceived fatigue will be asked just before and immediately after the test using the VAS-F (see Figure 4). Furthermore, a short structured interview will follow including the following question: "On a scale from 0 to 100, how certain are you that you have been precise/accurate in detecting ongoing variations in your performance? Please mark your confidence level on the presented visual scale". This question is then followed by an open-ended question where the participant is asked to report on which sensory information he/she was relying to gauge performance variations and give the reports: "On which aspects of your motor performance where you paying attention to detect variations and decide to give a report during the task? Please list them here".

[figure not shown]

Figure 7 Visual scale for confidence rating: subjective beliefs on their perceptive accuracy

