## Task 2: Perceptive accuracy for STS duration variations during repeated STS postural transitions

The participants will be tested on a armless chair of normalized seat height, for their ability to accurately perceive changes in their self-paced sit to stand duration.

They will be instructed to perform STS repetitions at a fixed pace, but to execute each transition from sitting to standing as fast as possible. Sitting with the back rested on the back-support will be the starting position of the test. After the first STS transition (i.e. starting from the first standing position), they will be presented with a countdown of 10 seconds during which they must return to the sitting position and, from that position, perform the following STS transition. The participant will be asked to use the time in between STS repetitions to evaluate their sit-to-stand duration, comparing it with the previous, and decide if to report (or not) a change in STS duration (using the same handheld sensor as during the 6MWT). The STS execution will be stopped by the examiner after 36 repetitions.

Neutral instructions will be provided to the subject before starting the STS test by reading the following script: "When you will hear the beep tone, squeeze the sensor and start performing sit-to-stand repetitions, doing each of them standing up at the maximal speed that you can use to stand up safely. Be aware that we are not asking you to perform as many repetitions you can in a limited amount of time, but that you will be asked to stand up from the chair once every 10 seconds, you just have to do each repetition at your maximal speed: going from sitting to standing as fast as you can. Natural variations in your sit-to-stand speed may occur between repetitions. We want you to notice and, starting from the second repetition, report them using the handheld sensor: if you perceived a change in the time needed to stand up, being it shorter or longer does not matter (you will not have to indicate it), squeeze the sensor in your hand during the resting phase. In between repetitions you will have 10 seconds to decide if to report a change: in the case you didn't notice any change, simply don't squeeze."

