Participants will be also equipped with headphones. Using the same set of wearable sensors, as in task 1 (6MWT overground), to detect motor performance will allow us to then confront the time and frequency of the reports with the actual STS duration variations, and propose novel outcome measures: a perceptive threshold for STS duration changes and the ratio between reporting frequency and actual STS duration variability, reflecting perceptive accuracy (see example plot from piloting in Figure 8). The intensity of perceived fatigue and a short structured interview will follow in the same way as in task 1 (6MWT overground).

[figure not shown]

Figure 8 Perceptive accuracy for STS duration variations during repeated STS postural transitions: Task 2 illustration, wearables placement and Perception vs Performance plot graphic illustration.

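### Part A gives no rule for participants who never report a change; their threshold is right-censored, and leaving them out of the t test can bias the group comparison

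*Combined protocol and SAP*

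**What the plan says.** For the overground walk, the section on Task 1 of Part A defines the threshold as "the change in speed at the first report as a perceptive threshold for overground walking speed changes, informing on the minimal clinically important change". The section on Task 2 only names "a perceptive threshold for STS duration changes and the ratio between reporting frequency and actual STS duration variability", with no computing rule for the threshold. No threshold is defined for the smoothness runs.

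Both tasks treat silence as an answer. In Task 1, "the action of holding the sensor, without squeezing it, confirms that the participant is not perceiving any change in speed". In Task 2 the script says "In between repetitions you will have 10 seconds to decide if to report a change" and "in the case you didn't notice any change, simply don't squeeze"; the smoothness script for STS repeats this. Direction is not collected in the walk: "being them accelerations or decelerations, this information does not matter for our test". Both scripts also ask for a squeeze at the start tone, and the text does not say that this squeeze is excluded when the first report is identified.

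Under Data and statistical analysis, the plan takes the "minimal perceptive threshold for self-paced performance variations which will be compared between groups with an independent T test", followed by a non-parametric alternative in brackets. No section gives a value, rank or censoring rule for a participant with no reports. The only provision for missing values is the 10% added to 40 per group under Participants.

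**The concern.** A participant who attends throughout and never squeezes has complied fully, so this is not ordinary missing data. The run shows that their threshold exceeds the largest change they made. A t test cannot use a lower bound, and a Mann-Whitney test cannot use it either unless someone assigns a rank.

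Run as written, the comparison is therefore restricted to people who noticed something. Those removed tend to be the least perceptive, and the Part A hypotheses expect poorer perception in PwMS with more fatigue. The group contrast may then be biased, and whoever analyses the data would have to choose a rule after seeing who did not report.

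A smaller matter is interpretation. The task asks whether a change was noticed and never whether it mattered, so a threshold from it does not inform a minimal clinically important change.

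**Working it through.** **1. The plan's own figure.** 40 × 1.10 = 44 per group, as stated (40/0.90 = 44.4, so 45, by the other convention). The 40 cannot be reproduced, because no effect size, SD, power or sidedness is given. As a benchmark, 40 per group at two-sided 0.05 detects 0.634 SD with 80% power; at 0.65 SD the full-data t test has 82%.

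**2. What is observed.** Let T be a person's threshold and M the largest change they make in the run. They report if M > T. A reporter supplies T. A non-reporter supplies only T ≥ M. A test on reporters compares mean T given T < M, which depends on M as well as on T.

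**3. Size, with the same M in both groups.** All inputs here are assumptions: log T normal with SD 0.5, PwMS higher by 0.65 SD (0.325 log units), log M normal with SD 0.5, 40 per group. The non-reporting probability is Φ((mean log T − mean log M)/√(0.5² + 0.5²)). For example, with mean log M 0.75 above the controls' mean log T:
- controls: Φ(−0.75/0.707) = Φ(−1.06) = 14%
- PwMS: Φ((0.325 − 0.75)/0.707) = Φ(−0.60) = 27%

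Simulated results (true difference 0.65 SD):

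| Non-reporters, controls/PwMS | Difference among reporters | Power, t test on reporters | Power, Gehan test |
|---|---|---|---|
| 2%/5% | not tabulated | 77% | 79% |
| 4%/9% | 0.58 SD | 75% | 80% |
| 14%/27% | 0.51 SD | 61% | 77% |
| 24%/40% | about 0.49 SD | 53% | 73% |

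In the third row the difference falls by 1 − 0.51/0.65 = 22%. Repeat runs with 3,000 studies move the power figures by about 2 points.

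**4. A harsher loss model.** Suppose everyone above one fixed ceiling fails to report, with a true difference of 0.634 SD. Then 2%/9% non-reporters give 0.516 SD and 69% power, and 7%/19% give 0.432 SD and 57%. Ranking non-reporters worst in a Mann-Whitney test keeps power at 77% in both cases. The size therefore depends on the model as well as on the rate.

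**5. PwMS also make larger changes.** If M is shifted by the same 0.65 SD in PwMS, non-reporting is equal at 15%/15%, the difference among reporters stays at 0.65 SD, and power is 84% for the t test against 79% for Gehan. At 24%/24% it is 81% against 76%.

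**6. Would averaging all reports be better?** Assume equal thresholds in the two groups, with changes 20% more variable in PwMS. The test should reject 5% of the time. It rejects 24% of the time for the first report and 73% for the mean over all reports. Every reported change lies above threshold, so the average rises with a person's own variability, and averaging makes that confounding more precise.

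**The case against.** The plan does not say that non-reporters are dropped. It is silent, and an analyst using the rank test could place them last. That is true, and exclusion is a consequence of the silence, not a stated rule. The bracketed alternative is no rule either: it is triggered by a normality test, and it needs an assigned rank to include anyone without a value.

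Non-reporters may be rare. Participants practise with the device, are told that variations may occur, and have six minutes or up to 35 decisions (36 repetitions, reporting from the second). This stands: at 2%/5% the loss is trivial.

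A reader might infer that omission must hide a group difference. The documents do not support that. The introduction says that many PwMS deteriorate during sustained activity, so they may make larger changes, and step 5 then shows no attenuation.

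A reader might also infer that one event per run is too noisy and that all reports should be averaged. The documents give no reliability figure, and step 6 shows that the average is not a threshold. Nor do they show that first reports come early, or that calling the threshold minimal in the analysis section conflicts with the first-report definition; it can simply mean the smallest perceptible change.

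Finally, the study calls itself exploratory, its Part A hypotheses concern accuracy without naming the threshold, and the outcome relating report frequency to variability uses every report. These points limit the weight of the problem but do not supply the missing rule.

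**Conclusion.** The concern holds in this form: the Part A threshold has no value for a participant with no reports, such participants are right-censored, and a comparison restricted to reporters can be biased. With similar self-paced changes in both groups and more non-reporting in PwMS, the loss runs from almost nothing at 2%/5% to about 20 points of power (53% against 73%) at 24%/40%. With larger changes in PwMS, the t test may lose nothing and the censored test costs a few points.

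All rates, SDs and the 0.65 SD effect are assumptions. They illustrate the mechanism and correct no stated power figure. The first-report definition is explicit only for walking speed. The frequency-to-variability outcome is not affected. The wording on clinical importance is unsupported by the task, though no analysis is attached to it.

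**What to change.** Before the data are examined, amend the analysis section as follows.

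- Keep the change at the first report as the threshold. Define it in the same way for the STS run, state the reference from which the change is measured, and exclude the squeeze at the start tone.
- Treat a participant with no report as right-censored at the largest change made without a report.
- Compare groups with a rank test for censored data (Gehan) or a Tobit model on the log scale. Unlike a blanket worst rank, these allow for a non-reporter who made only small changes.
- Report the number of non-reporters per group, and give the reporters-only test as a sensitivity analysis.
- Do not replace the first report with the mean over all reports. The first report is also somewhat sensitive to a person's variability (24% against 5% in step 6), so show each group's variability beside the threshold result.
- Describe the result as a noticed change and delete the reference to minimal clinically important change.

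The cost is some SAP wording, a few lines of code and, in some scenarios, a few points of power. No new data or participants are needed.
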